# Table 10. One-stage stopping rule for treatment-related mortality for patients treated at the RP2D

Decision Rule	Action
$\geq$ 3 transplant-related deaths out of 20 patients	Trial termination recommended.
$\leq$ 2 transplant-related deaths out of 20 patients	Uproleselan is safe for further investigation in pediatric patients

This one-stage rule has 92.5% power with an 9.1% type 1 error rate to test the null hypothesis that P>0.25 versus the alternative that P<0.05, where P is the probability of a transplant-related
death. The choice of the null and alternative hypothesis is based on an observed non-relapse mortality of 10.3% at 3 years for the BFC trial of pediatric patients in the Netherlands.

## 13.52 Monitoring rule for RRT

A one-stage stopping rule will monitor regimen-related toxicity (RRT) for the N=20 patients treated at the RP2D. RRT is defined as the occurrence of dose limiting toxicities as outlined in Table 4, from Day -7 pre-transplant to post-transplant Day +30.

The one-stage interim monitoring rule RRT is presented in Table 11. If there are 3 or more patients with dose limiting RRT in the 20 patients treated at the RP2D, enrollment to the trial will be suspended so that DSMC can consider terminating the trial. If there are 2 or fewer patients with RRT in the 20 patients treated at the RP2D, this is evidence in support of safe use of uproleselan for further investigation in pediatric patients.

The choice of the null and alternative hypothesis is derived from two early phase clinical trials of conditioning with busulfan and a purine analogue. In a trial of fludarabine and busulfan in adolescents and adults transplanted for hematologic malignancies, where busulfan exposure was escalated, 5 of 40 patients (12.5%) receiving busulfan targeted to an average AUC 6, 000  $\mu$ Molmin developed grade 4 regimen related toxicity (based on CTCAE criteria, mucositis and/or transaminitis){Perkins, 2012 #76}. In a phase 1/2 trial in children and adults transplanted for hematologic malignancies, 1 of 22 patients (4.5%) receiving fludarabine 10 mg/m2, clofarabine 30 mg/m2 and busulfan targeted to an average AUC 6, 000  $\mu$ Molmin developed grade 4 regimen related toxicity (based on CTCAE criteria){Andersson, 2011 #59}.

Decision Rule	Action		
≥3 RRTs out of 20 patients	Trial termination recommended.		
≤2 RRT out of 20 patients	Evidence supports safety of uproleselan for		
	further investigation in pediatric patients		

 Table 11. One-stage stopping rule for RRT for patients treated at the RP2D

This one-stage rule has 94% power with an 9.3% type 1 error rate to test the null hypothesis that P>0.185 versus the alternative that P<0.020, where P is the probability of a transplant-related death. The choice of the null and alternative hypothesis is based on sinusoidal obstruction syndrome accounting for the majority of severe RRT in HSCT and an expected incidence of severe VOD of approximately  $10\%^{35}$ 

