Importantly, BFC has been extended to a large group of children and adolescents at the Leiden University Medical Center and University Medical Center Utrecht transplant centers in the Netherlands. 155 children (median age 9.7 years) with hematologic malignancies were enrolled, including 69 with AML (28 in CR1, 40 in CR2, 1 with active disease). 119 patients received transplants from unrelated donor. Most patient received either bone marrow (n=79) or cord blood (n=66) grafts. There were only 2 cases of non-engraftment. Non-relapse mortality at 3 years was 10.3%. No veno-occlusive disease of the liver was observed. The cumulative incidence of relapse in AML was 22.5% and event free survival for patients transplanted in AML in 1st CR and 2nd CR was 64% and 65%, respectively. These results demonstrate that in pediatric patients BFC is safe, well suited for cord blood transplantation and effective for AML.

BFC was chosen for use as the conditioning backbone in this trial because it may be more effective in patients with chemotherapy-resistant AML, because it is safe in pediatric patients and because it is immunosuppressive enough to produce robust engraftment in cord blood transplantation.

The current trial builds on other recent attempts to add novel chemotherapy agents to BF or BFC conditioning in adults with AML. The list of agents that have been tested or are currently being tested in early phase trials includes plerixafor, CPX-35121 and vorinostat (NCT02083250).

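### The RRT stopping rule in Section 13.52 quotes the error rates of a different boundary, and neither of its two stated sources supports the 2% alternative

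*Protocol*

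**What the plan says.** The rule is set out in Protocol Section 13.52 and Table 11: "A one-stage stopping rule will monitor regimen-related toxicity (RRT) for the N=20 patients treated at the RP2D". The boundary reads: "If there are 3 or more patients with dose limiting RRT in the 20 patients treated at the RP2D", in which case enrollment is suspended and the DSMC considers termination. With 2 or fewer, the result counts as support for safety.

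The stated performance is: "This one-stage rule has 94% power with an 9.3% type 1 error rate", "to test the null hypothesis that P>0.185 versus the alternative that P<0.020". The same sentence defines P as the probability of a transplant-related death, although the rule counts toxicities.

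The origin of the two hypotheses is given twice.

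- Before Table 11: "The choice of the null and alternative hypothesis is derived from two early phase clinical trials". The trials are a fludarabine-busulfan study with grade 4 toxicity in 5 of 40 (12.5%) and a fludarabine-clofarabine-busulfan study with 1 of 22 (4.5%), both by CTCAE.
- After Table 11: "The choice of the null and alternative hypothesis is based on sinusoidal obstruction syndrome accounting for the majority of severe RRT in HSCT", together with an expected severe VOD incidence of about 10%.

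**The concern.** A stopping rule is read through three things: the boundary, the rates it is meant to separate, and the error rates that follow. In Section 13.52 these do not fit together.

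The two accounts of the hypotheses use different sources and endpoints and imply different toxicity levels, and neither shows how 2% was reached. Power is nevertheless quoted at 2%, a rate lower than any the section cites.

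In addition, the error rates do not match the printed boundary. Because the null is that toxicity is too high, a type 1 error here means declaring support for safety when the true RRT rate is 18.5%. That is the error a safety rule should state correctly.

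**Working it through.** **Inputs.** From Section 13.52: n = 20; pass at 2 or fewer; null rate 0.185; alternative rate 0.020; stated power 94%; stated type 1 error 9.3%; cited rates 4.5%, about 10% and 12.5%.

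**Formula.** With X the number of patients with RRT, X ~ Binomial(20, p). A rule that passes at r or fewer has type 1 error P(X ≤ r | 0.185) and power P(X ≤ r | 0.020).

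**Check of the method on the TRM rule (Section 13.5, Table 10).** With r = 2, null 0.25 and alternative 0.05, P(X ≤ 2) is 0.0913 and 0.9245. The protocol states 9.1% and 92.5%, so exact binomial is evidently the method in use.

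**The RRT rule.**

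- At p = 0.02: P(0) = 0.98^20 = 0.6676; P(1) = 20 × 0.02 × 0.98^19 = 0.2725; P(2) = 190 × 0.02² × 0.98^18 = 0.0528. So P(X ≤ 1) = 0.9401 and P(X ≤ 2) = 0.9929.
- At p = 0.185: P(0) = 0.815^20 = 0.0167; P(1) = 20 × 0.185 × 0.815^19 = 0.0759; P(2) = 190 × 0.185² × 0.815^18 = 0.1637. So P(X ≤ 1) = 0.0926 and P(X ≤ 2) = 0.2563.

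The stated pair (94%, 9.3%) is reproduced by r = 1, stopping at 2 or more. The printed rule, r = 2, gives 99.3% and 25.6%. No other cut-off from r = 0 to r = 3 at n = 20 gives the stated pair.

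**Where 2% and 18.5% could come from.**

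- From the two trials: 5/40 = 12.5% and 1/22 = 4.5%. Both exceed 2%, and no step links either figure to the hypotheses.
- From VOD: if severe VOD is about 10% and makes up more than half of severe RRT, total severe RRT is at least 10% and below 10%/0.5 = 20%. A rate of 18.5% fits, since VOD would then be 0.10/0.185 = 54% of RRT. A rate of 2% does not fit.

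**Probability of passing, by true RRT rate.**

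| True rate | Stop at 3 or more (printed) | Stop at 2 or more (matches stated error rates) |
|---|---|---|
| 2% | 99.3% | 94.0% |
| 4.5% | 94.1% | 77.3% |
| 10% | 67.7% | 39.2% |
| 12.5% | 53.5% | 26.7% |
| 18.5% | 25.6% | 9.3% |

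**The case against.** Several stronger readings are tempting, and the documents do not support them.

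**That the rule will often recommend termination when uproleselan adds nothing.** The printed rule stops with probability 32.3% at 10% and 46.5% at 12.5%. But the only cited trial with this conditioning backbone is the 4.5% one, where the printed rule passes 94.1% of the time. The 12.5% comes from a regimen without clofarabine in which busulfan exposure was escalated. Nor are the trial rates on the trial's own scale. Table 4 uses Seattle grade 3 or more for most organs and grade 2 or more for the nervous system, while the two trials report CTCAE grade 4. The 12.5% consisted of mucositis and/or transaminitis; in Appendix D a transaminase rise alone reaches at most hepatic grade II, and oral grade III needs preventive intubation or aspiration pneumonia. The lower nervous system threshold works the other way. The true background RRT rate is therefore unknown.

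**That the 18.5% null is also unsupported.** It lies inside the range that the VOD statement implies. Only its derivation is missing.

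**That Section 2.3 contradicts the 10% VOD figure.** Of a pediatric series on the same backbone, that section says: "No veno-occlusive disease of the liver was observed". This is an observed result in children with mixed hematologic malignancies. Section 13.52 gives a planning figure from another source, for a trial limited to refractory or MRD-positive AML. Both can be true.

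**That the quoted power conceals the risk from the DSMC.** The cited rates stand in the same section, the committee includes a biostatistician, and crossing the boundary leads to a review, not automatic closure.

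A further defence is that the protocol simply brackets background rates. The TRM rule does so too, with 5% and 25% around a cited 10.3%. An alternative below background is a legitimate choice, and 1 event in 22 does not exclude 2%: at that rate, at least one event occurs with probability 1 − 0.98^22 = 1 − 0.6412 = 36%. What remains is that Section 13.52 says its alternative is derived from its sources, and no derivation to 2% is given. None of these points touches the mismatch between boundary and error rates.

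**Conclusion.** The point holds on two counts.

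First, the stated operating characteristics are wrong for the rule as printed. At 18.5% the type 1 error is 25.6%, about 2.8 times the stated 9.3% (25.6/9.3), while power at 2% is 99.3%, above the stated 94%. This rests only on 20 independent patients with a common RRT probability, the model that reproduces the TRM figures. The document does not show whether the boundary or the error rates are in error.

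Second, the hypotheses have two different stated sources, and neither supports 2%. How much this costs depends on the true background RRT rate, which the protocol does not give on its own scale. The pass probabilities between 4.5% and 12.5% show how sensitive the rule is; they do not predict what it will do. Labelling P as a death probability is a plain error.

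**What to change.** 1. Reconcile the boundary in the text and Table 11 with the stated error rates. As they stand, one of them must change; the sponsor has to say which was intended.
2. Keep one derivation of the hypotheses. State the acceptable RRT rate, show how it follows from the chosen source, and acknowledge that the two trials' CTCAE grade 4 rates are not the Table 4 endpoint.
3. Define P as the probability of dose-limiting RRT.
4. Replace the single power statement with the probability of passing the final rule at 2%, 4.5%, 10%, 12.5% and 18.5%, marking the three middle rates as sensitivity values.

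The cost is a short text amendment and one small table, with no change to the sample size. If the printed boundary stays, the protocol must own a 25.6% chance of passing an 18.5% toxicity rate. If the stated error rates stay, the boundary becomes stricter, and the chance of passing at 4.5% falls from 94.1% to 77.3%.

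### The error rates printed for the RRT stopping rule belong to a stricter cut-off: as written, the rule has 25.6% type 1 error and 99.3% power, not 9.3% and 94%

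*Protocol*

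**What the plan says.** Section 13.52 of the protocol introduces the rule: "A one-stage stopping rule will monitor regimen-related toxicity (RRT) for the N=20 patients treated at the RP2D". It then gives both sides of the boundary:

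- "If there are 3 or more patients with dose limiting RRT in the 20 patients treated at the RP2D", enrollment is suspended so that the DSMC can consider ending the trial.
- "If there are 2 or fewer patients with RRT in the 20 patients treated at the RP2D", the result counts as evidence that uproleselan is safe enough to study further.

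Table 11 repeats the same boundary, 3 or more against 2 or fewer. Below the table, the section reports that the rule "has 94% power with an 9.3% type 1 error rate to test the null hypothesis that P>0.185 versus the alternative that P<0.020", and adds "where P is the probability of a transplant-related death".

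Section 13.51 has a companion rule for transplant-related mortality (TRM), also with 20 patients and a boundary between 2 and 3. Under Table 10 the protocol says of it: "This one-stage rule has 92.5% power with an 9.1% type 1 error rate to test the null hypothesis that P>0.25", against an alternative of P<0.05.

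**The concern.** The two rules share the same sample size and the same cut-off, but the RRT rule has a lower null rate (0.185 against 0.25). With a lower null rate, 2 or fewer events is more likely under the null, so the RRT rule should have a clearly larger type 1 error than the TRM rule. The protocol prints almost the same value for both, 9.3% and 9.1%. That alone shows that something in Section 13.52 does not fit.

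What is at stake is the description of a safety rule. RRT is one of the two components of DLT (Section 5.3), and DLT is the Phase 2 primary endpoint (Section 13.2.1). Section 2.1.3 describes the trial as the first of this drug in children and the first in transplantation. Type 1 error here is the chance of recording support for safety when the RRT rate is at the level set as the null. A figure that is too low makes the rule look more protective than it is.

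**Working it through.** **Inputs, all from the protocol.** n = 20; support for safety if X ≤ 2 (Section 13.52 text and Table 11); null boundary p0 = 0.185; alternative boundary p1 = 0.020; stated type 1 error 9.3% and power 94%.

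**Formula.** With X binomial(20, p), rejecting the null means X ≤ c. Type 1 error is P(X ≤ c | p0) and power is P(X ≤ c | p1), where

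P(X ≤ 2 | p) = (1−p)^20 + 20·p·(1−p)^19 + 190·p²·(1−p)^18.

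**Step 1: confirm the protocol's method on the TRM rule (Section 13.51, c = 2).**

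- p = 0.25: 0.0032 + 0.0211 + 0.0669 = 0.0913 after rounding (printed 9.1%).
- p = 0.05: 0.3585 + 0.3774 + 0.1887 = 0.9245 after rounding (printed 92.5%).

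Both figures reproduce, so the protocol's convention is the exact binomial with these definitions.

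**Step 2: apply the same method to the RRT rule as written (c = 2).**

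- p = 0.185: 0.0167 + 0.0759 + 0.1637 = 0.2563.
- p = 0.020: 0.6676 + 0.2725 + 0.0528 = 0.9929.

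Neither matches the printed 9.3% and 94%.

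**Step 3: find what the printed pair describes.**

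| Support for safety if | P at 0.185 | P at 0.020 |
|---|---|---|
| X ≤ 0 | 0.0167 | 0.6676 |
| X ≤ 1 | **0.0926** | **0.9401** |
| X ≤ 2 (as written) | 0.2563 | 0.9929 |
| X ≤ 3 | 0.4792 | 0.9994 |

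Only the 1-or-fewer row gives both printed values.

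**Step 4: rule out other explanations.**

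- *Approximations at c = 2.* The Poisson gives 0.285 and 0.992. The normal gives 0.164 and 0.995, or 0.245 and 0.9996 with continuity correction.
- *Another sample size.* At n = 28 the type 1 error comes near the printed value (0.087), but power is then 0.982. No n from 15 to 39 gives both figures at c = 2.
- *Other hypotheses.* Keeping c = 2 and n = 20, a 9.3% type 1 error needs a null of about 0.249, and 94% power needs an alternative of about 0.045. Neither is the printed value.

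**Step 5: size.** 0.2563 / 0.093 = 2.76. At p = 0.185 the chance that enrollment is suspended is 1 − 0.2563 = 74.4%; the printed rate implies 1 − 0.093 = 90.7%. Power is understated by 99.3 − 94 = 5.3 percentage points.

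**The case against.** The strongest reply is that little in the conduct of the trial turns on these two percentages. The trigger is stated the same way in the text and in Table 11, so sites and the DSMC can apply it without doubt. In the text, crossing it leads to DSMC consideration, not automatic termination, and staying below it is described only as supporting evidence. The DSMC also reviews all adverse events and deaths at regular intervals (Section 12.2), the TRM rule runs alongside, and the Phase 2 toxicity analysis is descriptive (Section 13.6). The protocol does not say that the cut-off was chosen from these error rates or that anyone relies on them. Nor is the error all in one direction, since power is understated too. The reference to death in the definition of P looks like wording carried over from Section 13.51 and changes no number.

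Most of this is fair, and it limits the consequence: if the written cut-off is the intended one, no patient is managed differently because of the misprint. It does not make the figures right. They are the only operating characteristics given for this rule, and the DSMC reviews the protocol before activation. The document also does not show which element is the slip. If the cut-off is the error, the safety boundary itself is affected.

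**Conclusion.** The concern holds. The cut-off in Section 13.52 and Table 11 and the error rates printed below it describe two different rules. With 20 patients and independent outcomes at a common rate, the rule as written has 25.6% type 1 error at 0.185 and 99.3% power at 0.020. The 2.8-fold understatement of type 1 error assumes that the written cut-off and hypotheses are the intended ones; the protocol does not settle that. Under the other reading, the printed rates are right and the boundary in the text and table is not the one they describe. Both readings require a correction. The definition of P as a probability of death is a separate wording error in the same sentence and adds nothing to the size of the problem.

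**What to change.** Reconcile the cut-off, the hypotheses and the error rates in Section 13.52 and Table 11.

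- **If the written cut-off and hypotheses are kept:** restate type 1 error as 25.6% and power as 99.3%. This is one sentence, with no extra patients and no change in conduct. The cost is that the disclosed type 1 error is less favourable.
- **If 9.3% and 94% were intended with these hypotheses:** the text and Table 11 do not match them, and the sponsor and DSMC must decide which governs. Moving the boundary changes conduct and would be a substantive amendment. The protocol states no expected overall RRT rate, so the effect is shown over assumed rates borrowed from figures that Section 13.52 cites for related outcomes (grade 4 toxicity in two trials, and severe VOD):

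| Assumed RRT rate | P(3 or more of 20) | P(2 or more of 20) |
|---|---|---|
| 4.5% | 5.9% | 22.7% |
| 10% | 32.3% | 60.8% |
| 12.5% | 46.5% | 73.3% |

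- **If the null or alternative rate is changed instead:** give the new rates their own justification and recompute both error rates.

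In every case, define P in Section 13.52 as the probability of a dose-limiting RRT.

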## 13.6 Analysis of Primary Endpoints

To address primary objective in section 1.3 Phase 1, the RP2D will be identified through the application of the 3+3 design. Accrual will be temporarily suspended after the enrollment of each cohort of 3 patients on a dose level, until all 3 patients have either completed the DLT observation period (30 days) or experienced a DLT.

To address primary objective in section 1.3 Phase 2, all observed toxicities will be summarized

using frequencies, proportions, and 95% confidence intervals by type (organ affected or laboratory determination), severity (by CTCAEv5.0), attribution, and expectedness. Only the maximum grade for each type of toxicity will be tabulated for each patient.

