# **1.3 Primary Objectives**

Phase 1. To assess the safety and tolerability and identify the recommended phase 2 dose (RP2D) of uproleselan when combined with myeloablative, busulfan-based, pre-transplant conditioning regimens for treatment of acute myeloid leukemia.

Phase 2. To describe the safety of uproleselan at the RP2D when combined with myeloablative, busulfan-based, pre-transplant conditioning regimens for treatment of acute myeloid leukemia.

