# 7.1 Expected Toxicities

# 7.1.1 Adverse Event List for Uproleselan

The adverse events observed with uproleselan in the phase 1/2 clinical trial of uproleselan combined with induction chemotherapy did not differ in type or frequency from those associated with AML induction chemotherapy alone. Likewise, no toxicities have been observed in animal studies. As mentioned, because the drug has been shown to protect normal hematopoietic stem cells from the cytotoxicity of chemotherapy, there is a concern that it could impede engraftment of donor hematopoietic stem cells.

In A Phase I/II, open-label, multicenter trial (GMI-1271-201) as an adjunct to standard chemotherapy in 91 subjects with AML patients were enrolled in both the relapsed/refractory and newly diagnosed populations and added uproleselan to standard induction chemotherapy (MEC or cytarabine + idarubicin '7+3'), with the option in Phase II for consolidation (uproleselan plus chemotherapy) in patients who responded to treatment. In the relapsed/refractory patient population, no additive toxicity was detected and the adverse event (AE) profile was consistent with that normally observed with cytarabine-based chemotherapy. The safety profile observed in the elderly newly diagnosed patient population suggested no additive toxicity in this more vulnerable group (refer to the uproleselan IB). Collectively, the treatment of AML in adult patients up to 75 years of age was not found to raise any concerns for the safety profile of uproleselan when combined with 2 different cytarabine-based induction regimens. Further, while more limited, the patient experience with cytarabine-based consolidation and uproleselan appears to be consistent with this profile.

7.1.2 Adverse Event List for Allogeneic HSCT with Busulfan, Fludarabine, Clofarabine Conditioning with Tacrolimus and Methotrexate or Myecophenolate Mofetil GVHD Prophylaxis.

There are many expected AEs of the treatment that uproleselan is being incorporated into. These include, but are not limited to, serious bacterial, viral and fungal infections, veno-occlusive disease of the liver, acute kidney injury, thrombotic microangiopathy, oral and gastrointestinal mucositis, idiopathic pneumonia syndrome, encephalopathy, bleeding, dermatitis, and GVHD. These and other toxicities known to occur in HSCT using these forms of conditioning and GVHD prophylaxis are considered expected.

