## 7.3 Adverse Event Collection

All Grade 3 and higher non-hematologic adverse events occurring through transplant day +30 (regardless of attribution or expectedness) will be routinely reported. Routine reporting is accomplished via the Adverse Event (AE) Case Report Form (CRF) within the study database. Adverse events that require collection are defined in Tables 5 and Table 6 and must be reported in routine study data submissions on the toxicity case report forms. This includes adverse events previously reported in an expedited manner (see section 7.5).

Table 5. Hematologic Adverse Event Routine Collection Requirements					
Grade 1-4	Short-term, reversible grades 1-4 hematologic laboratory abnormalities are				
	expected during transplant and do not require collection or reporting.				
Grade 5	All grade 5 AEs should be collected and reported.				

Table 6. Non-Hematologic Adverse Event Routine Collection Requirements				
Grade 1	Grade 1 AEs do not need to be collected unless they otherwise meet criteria			
	for a serious adverse events (SAE) as described in Section 7.4.			
Grade 2	Unexpected grade 2 AEs will be collected with the following exceptions:			
	• Abnormal laboratory values or test results that are not associated with			
	clinical signs or symptoms and are not considered clinically significant			
	(i.e., require no treatment or further diagnostic testing)			
Grade 3	All grade 3 non-hematologic AEs should be collected and reported.			
Grade 4	All grade 4 non-hematologic AEs should be collected and reported.			
Grade 5	All grade 5 non-hematologic AEs should be collected and reported.			

Between Day +30 - Day +100 the following adverse events should be collected and reported to the Sponsor:

- Events that are deemed to be Serious and Unexpected
- The following adverse events of special interest would be deemed SAEs: VOD/SOS; graft failure; graft rejection; and > or = grade 3 pulmonary toxicity per CTCAE criteria.

These events should be reported to the Sponsor Investigator within 5 business days of discovery.

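### The maximum-grade rule in 13.6, read literally, drops unexpected (and sometimes related) toxicities from the Phase 2 safety table when the same organ has a worse event of the other class

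*Protocol*

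**What the plan says.** The Phase 2 primary objective (1.3) is descriptive and concerns the drug when added to busulfan-based conditioning: "To describe the safety of uproleselan at the RP2D when combined with myeloablative". Section 13.6 ties the toxicity summary to it: "To address primary objective in section 1.3 Phase 2, all observed toxicities will be summarized". How the summary is laid out comes next in that section: "using frequencies, proportions, and 95% confidence intervals by type (organ affected or laboratory determination), severity (by CTCAEv5.0), attribution, and expectedness". So type means an organ or a laboratory determination, not an individual CTCAE term. The paragraph closes with the reduction rule: "Only the maximum grade for each type of toxicity will be tabulated for each patient".

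Two other sections determine which events reach that table. In 7.3, Table 6 is selective at grade 2 for non-hematologic events: "Unexpected grade 2 AEs will be collected with the following exceptions". The exception is for laboratory or test abnormalities without clinical significance. From grade 3 upward it is not selective: "All grade 3 non-hematologic AEs should be collected and reported". Grades 4 and 5 are treated the same way. Section 7.1.2 describes the background: "There are many expected AEs of the treatment that uproleselan is being incorporated into". It goes on to name hepatic, renal, mucosal, pulmonary, neurologic and skin toxicities among them.

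**The concern.** The table is meant to be read by expectedness and by attribution, but the rule that picks the one event per patient and organ looks only at grade. The chosen event brings its own class with it, and any lower-grade event of the other class in that organ has no place in the table.

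This matters most for expectedness. Non-hematologic grade 2 events are routinely collected only when they are unexpected, while severe expected events are anticipated in the same organs. The protocol therefore goes out of its way to collect a group of events that its own summary rule can then leave out. At stake is the accuracy of the reported count of unexpected toxicity at the RP2D. The protocol (2.1.3) describes this trial as the first of the drug in children and the first in transplantation, and with 20 patients one or two missing cases change the reported picture.

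**Working it through.** **1. The plan's own precision figure.** Section 13.3 gives an exact 95% interval width of 0.379 for 20 patients at an observed proportion of 0.20. The Clopper-Pearson limits for x of n are the 0.025 quantile of Beta(x, n−x+1) and the 0.975 quantile of Beta(x+1, n−x). For 4/20 they are 0.0573 and 0.4366, width 0.3793. The figure reproduces and is not in dispute. It is used below only as a yardstick.

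**2. The rule applied to one patient.** Suppose a patient has an unexpected grade 2 gastrointestinal event and an expected grade 3 gastrointestinal event.
- Both are collected under Table 6.
- Both have the same type under 13.6 (same organ).
- The maximum grade is 3, so the single entry is grade 3, expected.
- The unexpected event adds nothing to the unexpected column at any grade.

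Replacing expected/unexpected with unrelated/related gives the attribution version.

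**3. Direction.** Compare the literal rule with a maximum taken within each class. If a patient's worst event in an organ belongs to a class, it is also that class's maximum, and both rules give the same entry. If it belongs to the other class, the literal rule gives no entry and the within-class rule gives one. So every entry in a class under the literal rule also appears under the within-class rule, and never the reverse. The class proportions can only be equal or too low.

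**4. Size, under assumption.** The documents give no masking rate. Let a be the share of patients with a lower-grade unexpected (or related) event in an organ. Let b be the share with a worse expected (or unrelated) event in the same organ, with a and b independent. For 20 patients:
- share tabulated = a(1−b)
- expected number masked = 20ab
- probability that at least one is masked = 1−(1−ab)^20

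For a = 0.20 (4 of 20 expected):

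| b | share tabulated | expected masked of 20 | P(at least one masked) |
|---|---|---|---|
| 0.10 | 0.18 | 0.4 | 0.33 |
| 0.30 | 0.14 | 1.2 | 0.71 |
| 0.50 | 0.10 | 2.0 | 0.88 |
| 0.70 | 0.06 | 2.8 | 0.95 |

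Over a from 0.10 to 0.30 and b from 0.10 to 0.70, the expected number masked per organ runs from 20 × 0.10 × 0.10 = 0.2 to 20 × 0.30 × 0.70 = 4.2.

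**5. What a reader of the table would see.** If 2 of 4 affected patients are masked, the table shows 2/20 = 0.10 (exact 95% CI 0.012 to 0.317) instead of 4/20 = 0.20 (0.057 to 0.437).

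**The case against.** The best defense is that the closing sentence of 13.6 exists only to stop repeat events in one patient being counted more than once, and that a programmer could apply it within each breakdown. Nothing in the section forbids that, and a statistical analysis plan could say so. This reading is possible, and under it nothing is lost. But it is not what the sentence says: the maximum is attached to type and patient, and to nothing else. An analysis plan that follows the protocol wording would inherit the problem. How ties in grade are handled is ordinary programming detail and is not pressed here.

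Three further points on the other side stand, and they limit the concern.

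- **Events do not vanish from the trial.** A reader might infer that masked events are recorded nowhere. Section 7.4 makes any unexpected, drug-related event an SAE. Section 7.5 requires expedited reporting of unexpected grade 2 or 3 events with at least possible attribution, and of unexpected grade 4 events whatever the attribution. Under 12.2 the DSMC receives tables of all reported SAEs, AEs and deaths.
- **These columns cannot isolate uproleselan.** A reader might infer that they would show a signal from the added drug. Section 7.2 says attribution and expectedness are judged for the combination as one study treatment. Toxicity from busulfan, clofarabine or fludarabine therefore also counts as related, so fewer events are likely to be classed unrelated. That weakens the attribution half of the point. The expectedness half keeps its force.
- **No decision rests on this table.** The Phase 2 primary endpoint is DLT occurrence (13.2.1). The 3+3, TRM and RRT rules (13.2.3 and 13.5) count DLTs, deaths and DLT-level toxicities directly.

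**Conclusion.** The concern holds in a limited form. Followed as written, 13.6 can understate unexpected toxicity, and less often related toxicity, in the descriptive summary assigned to the Phase 2 primary objective. The direction is certain under the literal reading. The size is not known: the figures above rest on assumed values of a and b and on their independence, and the 4/20 versus 2/20 comparison is an illustration, not an estimate. The documents do not support any claim that safety monitoring is compromised or that a uproleselan-specific signal is being hidden. It is a modest reporting defect, worth correcting before the tables are programmed.

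**What to change.** Replace the last sentence of 13.6 with wording to this effect: for the overall table, the maximum grade per patient and toxicity type is tabulated; for the tables by attribution and by expectedness, the maximum grade is taken separately among the events in each class, so a patient may be counted in more than one class.

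The cost is one sentence and one extra grouping step in the tabulation. No new data are needed, and sample size, monitoring and treatment are untouched. The one drawback is that class counts will no longer sum to the overall count, which a table footnote can explain.
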